3. RESEARCH DESIGN AND METHODS

3.1. Basic Study Design

The proposed study is a 4-year randomized trial to test the effectiveness of a novel treatment program for insomnia among women Veterans receiving outpatient care. The basic design is shown in **Figure 7**. As in our prior work, we will identify potential participants using a postal screening survey, including questions targeting ICSD diagnostic criteria for insomnia.⁴⁶ This survey will be sent to women who have received outpatient care (at least one visit) at the VA Greater Los Angeles Healthcare System (VAGLAHS) within the prior six months and live within a 50 mile radius of the Sepulveda Ambulatory Care Center (SACC) where the study will be conducted. Those who return the survey indicating symptoms of insomnia will be contacted by telephone to clarify study eligibility and to invite them for in-person screening/enrollment and baseline assessments. We anticipate enrolling a total of 400 women to achieve the proposed sample of 148 randomized participants (74 to receive ABC-I, and 74 to receive CBT-I).

[figure not shown]
Participants will complete a comprehensive sleep, mental health and physical health assessment at baseline (pre-treatment), immediately after the intervention ends (post-treatment), and 3 months after the end of the intervention (3-month follow-up). The primary outcomes will focus on differences in treatment adherence and attrition. We will also compare the effectiveness of the two interventions in terms of improving self-reported sleep quality and insomnia symptoms, plus objectively monitored sleep/wake patterns (wrist actigraphy) measured at post-treatment and at the 3 month follow-up using a non-inferiority design. Data will be analyzed both for treatment completers and for all randomized participants in an intention to treat analysis. Based on our recent work in this area, we expect to be able to enroll and randomize 148 women Veterans into the study within the proposed time frame. The planned research has been informed by our recently-completed HSR&D funded pilot study,⁴⁶ and our ongoing HSR&D funded intervention trial of CBT-I with older Veterans (PI: [name]).

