3.8. Data analysis plan

3.8a. Overview: Below we provide an overview of the study design considerations, and the analysis plan for each aim. We first present the approach for Aim 1, which involves traditional between-groups comparisons. Given the comparative effective approach required by Aims 2 and 3, we discuss these separately, and provide details regarding the structure of hypothesis testing for this method. In particular, we focus on the null hypothesis testing procedure and the determination of the clinically-meaningful effects (i.e., delta or δ) to be considered with respect to non-inferiority.

3.8b. Study Design Considerations: The equivalency of the two treatment groups at baseline is produced by the random assignment to groups. Randomization (combined with the ITT analysis strategy) should produce groups that differ only by chance with respect not only to factors related to study outcomes, and also to the outcomes themselves. Nevertheless, the adequacy of the randomization will be assessed by comparing the groups across outcomes measured at baseline. We will use a stratification based on hours of sleep reported on the postal survey (>6 versus ≤ 6 hours) to assign participants to strata for randomization. We have chosen stratified randomization to further increase the likelihood that the groups will be equivalent at baseline. The inclusion of covariates in such a situation would not be for the purpose of ensuring the comparability of the groups (because that comparability is created via randomization), but covariates may be used to enhance statistical power by reducing error variance.

We anticipate that some participants will not complete the intervention; however, we will continue to collect post-treatment and 3-month follow-up data, regardless of whether they complete the intervention program. Participants will be offered monetary incentives for providing post-treatment and follow-up assessments, regardless of whether they complete the intervention program to which they were assigned. We anticipate this will maximize the completeness of data; however, some data loss is unavoidable. In our recent study of older Veterans, we were able to obtain follow-up data for up to one year in 90% of randomized participants.

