24%	326	260	212	178	152	130	114
26%	436	336	268	218	182	154	134
28%	612	448	344	274	224	186	158

3.8d: Data analysis for Aims 2 and 3 (Hypothesis 2: ABC-I and CBT-I will be similarly effective in improving self-reported and objectively measured sleep from baseline to post-treatment; Hypothesis 3: ABC-I and CBT-I will be similarly effective in improving self-reported and objectively measured sleep from baseline to 3-months follow-up).

Two Step Hypothesis Testing of Non-inferiority: Hypotheses 2 and 3 seek to show that ABC-I is not inferior to CBT-I in terms of treatment effects (i.e., changes in sleep quality). Non-inferiority is established by framing the null

hypotheses in terms of the difference between the treatment means and comparing this difference to a pre-specified value, delta (δ), which represents the equivalence margin.

Determination of delta (δ): We elected to use a value of δ equivalent to an effect size of $d=0.40$. (i.e., 4/10ths SD). With respect to ISI, this represents a 2 point difference between the treatment effects. For PSQI, this represents a 1.4 point difference, and for actigraphically-estimated sleep percent, a difference of 5%.

Description of analysis: With respect to this study, non-inferiority is established by showing that the efficacy of ABC-I is no more than δ units less than CBT-I (**Table 12**).⁸⁸ This is tested by formulating a one sided null hypothesis that the difference between CBT-I and ABC-I is greater than or equal to δ (i.e., $H_0: \mu_{CBT-I} - \mu_{ABC-I} \geq \delta$) against the alternative hypothesis that the difference is less than δ (i.e., $H_A: \mu_{CBT-I} - \mu_{ABC-I} < \delta$). If the null

[figure not shown]
Table 12: Hypothesis testing in a non-inferiority study comparing ABC-I to CBT-I.

Type of study	Hypotheses	
	Null hypothesis (H_0)	Research Hypothesis (H_1)
Traditional comparative study	There is no difference between ABC-I and CBT-I	There is a difference between ABC-I and CBT-I
Non-inferiority study	ABC-I is inferior to CBT-I	ABC-I is not inferior to CBT-I (H₂ and H₃)

hypothesis is rejected, then the non-inferiority of ABC-I is established. For Aims 2 and 3, this two step process avoids the pitfall of erroneously interpreting a failure to reject the null hypothesis as evidence of no difference

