between the treatment groups. **Figure 8** illustrates four hypothetical patterns of results with respect to the outcome ISI using $\delta = 2$. In **Result 1**, the mean of CBT-I is greater than ABC-I and the confidence interval of this difference includes δ , and the noninferiority of ABC-I is not established. In **Result 2**, the mean of CBT-I is greater than ABC-I, however, the confidence interval excludes δ and the noninferiority of ABC-I is established. **Result 3** shows that the mean of ABC-I is greater than CBT-I and the confidence interval excludes δ , establishing the non-inferiority of CBT-I. **Result 4** shows that the mean of ABC-I is greater than the mean of CBT-I, however, the confidence interval includes δ so the noninferiority of ABC-I is not established.

Figure 8: Depiction of possible results for non-inferiority testing of ABC-I compared to CBT-I. The figure shows mean differences and 95% CI.

Statistical Analysis: To conduct the non-inferiority tests of Hypotheses 2 and 3, we will first use a 2 (group) by 3 (time) mixed model analysis of variance (ANOVA). The ABC-I vs. CBT-I groups will form the 2-level between groups factor, and the 3 time points (baseline, post-treatment, follow-up) will form the within groups factor. The null hypothesis will be that the differences between groups are greater than or equal to delta, as specified above, for ISI (2 points), PSQI (1.8 points) and sleep percent (5%).

Hypothesis 2 will compare the impact of the ABC-I to CBT-I at post-treatment (as compared to baseline) in terms of self-reported (ISI total score and PSQI total score) and objectively-measured (actigraphically-measured nighttime percent sleep) sleep quality variables. For each outcome measure, a 2 (group) by 3 (time) mixed model analysis of variance (ANOVA) will be performed. To directly test the impact of ABC-I vs. CBT-I on the change in outcomes from baseline to post-treatment, a planned interaction comparison will be tested that crosses treatment group (ABC-I vs. CBT-I) with time using a 1-1-0 contrast for the time factor). This interaction comparison will be used to directly test this hypothesis, that the ABC-I group shows greater positive changes (from baseline to post-treatment) on the outcome measures as compared to the CBT-I group.

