Hypothesis 3 will explore whether improvements seen at post-treatment are maintained over a 3-month follow-up time period. As with hypothesis 2, for each outcome measure, a 2 (group) by 3 (time) between/within analysis of variance (ANOVA) will be performed, but two interaction contrasts will be examined. The primary contrast of interest will examine impact of ABC-I (compared to CBT-I) on the change from baseline to 3 month follow-up by applying a -1 0 1 contrast to time and interacting that with treatment group. This interaction contrast will assess the impact of the ABC-I (compared to CBT-I) from baseline to the 3 month follow-up, assessing the persistence of the treatment effects. A secondary contrast will examine the change from post-treatment to six month follow-up by applying a 0 -1 1 contrast on time and interacting that with treatment group. This secondary comparison will assess differences in changes from post-treatment to 3 month follow-up for the ABC-I and CBT-I groups. Conceptually, this second contract will test whether there is either continued improvement after post-treatment (i.e., sleep is better at 3 months follow-up compared to post-treatment, or whether there is relapse (i.e., sleep is worse at 3 months follow-up compared to post-treatment).

Sample Size Calculations: For Aims 2 and 3, the required sample size was determined based on the minimum clinically-meaningful difference between the two treatments, rather than on the estimated effect size for an active treatment versus control condition. This non-traditional approach is required for comparative effectiveness designs.⁸⁸ To develop estimates of clinically-meaningful differences between treatments, we examined studies of CBT-I in the published literature.⁸⁹⁻⁹¹ We then considered clinically meaningful changes in ISI and PSQI scores and in objectively-measured sleep percent. We determined that a difference between the two treatment groups of more than 2 points on the ISI or PSQI, or more than 5% in objectively-measured sleep percent would constitute a clinically-meaningful difference between the treatments. This represents an effect size of approximately $d=0.40$ (that is, 4/10s of a standard deviation for each outcome measure). The required sample size (with alpha=.05 and .80 power) to detect for an effect size of 0.40 is n=138. We plan to randomize

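### The PSQI non-inferiority margin is 1.4 points where delta is set but 1.8 points in the null hypothesis, so a confidence limit between the two passes or fails depending on which paragraph is followed.

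*Combined protocol and SAP*

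**What the plan says.** Section 3.8a announces "the determination of the clinically-meaningful effects (i.e., delta or δ) to be considered with respect to non-inferiority", so the plan treats the clinically meaningful effect and the margin as the same quantity. Section 3.8d then gives a PSQI value in three places:

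- **Determination of delta:** the margin is set at d = 0.40 for every outcome, and "For PSQI, this represents a 1.4 point difference". The ISI margin is 2 points and the actigraphic sleep-percent margin is 5%.
- **Statistical Analysis:** the null hypothesis is that the groups differ by at least delta, "as specified above, for ISI (2 points), PSQI (1.8 points) and sleep percent (5"%).
- **Sample Size Calculations:** the clinically meaningful difference is "a difference between the two treatment groups of more than 2 points on the ISI or PSQI", described as approximately d = 0.40.

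Non-inferiority is declared when the confidence interval for the difference excludes delta. The caption of Figure 8 says "The figure shows mean differences and 95% CI", while the hypothesis itself is one-sided and the sample-size paragraph gives alpha as .05 without stating the number of sides. PSQI total score is one of three named outcomes for Hypothesis 2 (post-treatment), and the test is repeated for Hypothesis 3 (3-month follow-up).

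**The concern.** The null-hypothesis paragraph says it repeats a value already specified, and for the PSQI it does not. Both figures are called delta, for the same outcome and the same tests, so they are not two different quantities. A non-inferiority margin works only if it is a single number fixed in advance. Here a PSQI upper limit between 1.4 and 1.8 has no defined verdict, and the choice between the two paragraphs could be made after the result is known. The wider margin is 29% larger (1.8/1.4 = 1.29), which is more than rounding can explain.

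**Working it through.** **Side by side**

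| Place in 3.8d | ISI | PSQI | Sleep percent | SD implied for PSQI (value / 0.40) |
|---|---|---|---|---|
| Determination of delta | 2 | 1.4 | 5% | 1.4/0.40 = 3.5 |
| Null hypothesis | 2 | 1.8 | 5% | 1.8/0.40 = 4.5 |
| Sample-size paragraph | 2 | 2 | 5% | 2.0/0.40 = 5.0 |

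Only the PSQI column disagrees. At most one of its values can be exactly 0.40 SD of a single outcome. The third value is rounded and is not itself a tested null, so the direct conflict is 1.4 against 1.8.

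**The plan's own figure.** The only calculation given for these aims is a total of 138 for d = 0.40, alpha .05 and power .80. It is not specific to the PSQI. The usual formula, n per arm = 2(z₁₋α + z₀.₈₀)²/0.40², gives 77.3, so 78 per arm (156 in total) at one-sided 0.05, and 98.1, so 99 per arm (198 in total) at one-sided 0.025. Neither reproduces 138. That is a separate matter, and the margin conflict does not depend on it.

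**Inputs for the size of the effect.** 74 per arm (section 3.4c); margins 1.4, 1.8 and 2.0 (section 3.8d). The PSQI SD is not stated, so 3.5, 4.5 and 5.0 are assumed because they are what the three margins imply. The true difference is taken as zero.

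**Formulas.** SE = SD × √(2/74). Power at margin m is the probability that a noncentral t variable with 146 df and noncentrality m/SE exceeds the critical value, which is 1.655 at one-sided 0.05 and 1.976 at one-sided 0.025 (a two-sided 95% interval). Any result that passes at 1.4 also passes at 1.8, so the chance of opposite verdicts is power(1.8) − power(1.4).

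Example for SD 3.5 at one-sided 0.05: SE = 3.5 × √(2/74) = 0.575. The noncentralities are 1.4/0.575 = 2.43 and 1.8/0.575 = 3.13, giving power 0.781 and 0.929. The difference is 0.148.

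| SD | One-sided alpha | Power at 1.4 | Power at 1.8 | Power at 2.0 | Opposite verdicts, 1.4 vs 1.8 |
|---|---|---|---|---|---|
| 3.5 | .05 | 78% | 93% | 97% | 15% |
| 4.5 | .05 | 59% | 78% | 85% | 19% |
| 5.0 | .05 | 52% | 70% | 78% | 18% |
| 3.5 | .025 | 68% | 87% | 93% | 20% |
| 4.5 | .025 | 47% | 68% | 77% | 21% |
| 5.0 | .025 | 39% | 58%* | 68% | 19% |

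*0.585 before rounding.

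**Error rate.** If ABC-I is truly worse by exactly 1.4 points, testing against 1.8 leaves 0.4 points of slack. Non-inferiority is then declared with probability 17% (SD 3.5), 13% (SD 4.5) or 12% (SD 5.0) at a nominal 5%, and 10%, 8% or 7% at a nominal 2.5%.

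**The case against.** The best reply is that this is a slip of the pen. The paragraph headed as the determination of delta gives 1.4 and the null hypothesis defers to it, so the order of the text favours 1.4. That has some weight but does not settle the matter: the 1.8 stands in the hypothesis to be tested, and without an SD neither number can be checked.

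It can also be said that the 2-point figure is a joint, rounded statement about the ISI and PSQI. That is fair, and it is treated here only as a related mismatch.

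A third point concerns the remedy. The sample-size paragraph describes choosing a difference in points first and then noting that it is about 0.40 SD, so a margin fixed in points could be defended as well as one derived from an SD. This limits how far a reviewer can dictate the derivation. However, both paragraphs tie the margin to 0.40 SD, so deriving it that way follows the plan's own rule.

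Finally, the probabilities rest on SDs back-calculated from the disputed margins, on a true difference of zero, and on a simple comparison in place of the planned group-by-time contrast on change. They show scale and are not the trial's power. The contradiction itself needs no calculation.

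**Conclusion.** The concern holds. The plan gives two different PSQI margins for the same non-inferiority tests, 1.4 and 1.8 points, and nothing in it reconciles them. An upper confidence limit between them gives opposite conclusions whatever the SD. Under the stated assumptions (74 per arm, no true difference, SD 3.5 to 5.0), this happens in roughly one PSQI test in five to seven: 15 to 19% at one-sided 0.05, and 19 to 21% if the 95% interval is the rule. The documents do not establish which value was intended. The reach is limited: the ISI and sleep-percent margins are consistent, and section 3.1 says "The primary outcomes will focus on differences in treatment adherence and attrition", so the primary outcomes and the Aim 1 sample size are untouched. It should be fixed because it leaves one of the three Aim 2 and Aim 3 verdicts open to a choice made after the data are seen.

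**What to change.** Before any outcome is compared by arm:

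1. State the PSQI SD, its source, and whether it refers to raw scores or to change from baseline.
2. Derive one margin as 0.40 times that SD. If the sponsor prefers a margin fixed in points on clinical grounds, give that basis and report the effect size it represents.
3. Use that one number in the determination of delta, the null hypothesis and the clinically meaningful difference in the sample-size paragraph.
4. Restate PSQI power for that margin at the one-sided alpha or confidence level that will decide the verdict.

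The cost is wording only, with no change to conduct or enrolment. The restated power may fall short of the 80% quoted generically: a margin of exactly 0.40 SD with 74 per arm gives 78% at one-sided 0.05 and 68% at one-sided 0.025 in the simple calculation, whichever SD is chosen. That shortfall comes from the alpha level and the sample size, not from reconciling the margins.

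### Section 3.8d sets Hypothesis 2 up as non-inferiority, but the sentence saying what its contrast tests describes superiority

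*Combined protocol and SAP*

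**What the plan says.** Section 3.1 says that the sleep outcomes are "measured at post-treatment and at the 3 month follow-up using a non-inferiority design". The heading of section 3.8d words Hypothesis 2 as "ABC-I and CBT-I will be similarly effective in improving self-reported and objectively measured sleep from baseline to post-treatment". The paragraph on two-step testing adds "Hypotheses 2 and 3 seek to show that ABC-I is not inferior to CBT-I in terms of treatment effects".

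The description of the analysis says that "non-inferiority is established by showing that the efficacy of ABC-I is no more than" delta units below that of CBT-I, and that this is tested by "formulating a one sided null hypothesis that the difference between CBT-I and ABC-I is greater than or equal to" delta. Table 12 places Hypotheses 2 and 3 in its non-inferiority row. The first Statistical Analysis paragraph repeats the rule for both hypotheses: "The null hypothesis will be that the differences between groups are greater than or equal to delta, as specified above", with margins for ISI, PSQI and sleep percent.

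The next paragraph defines the Hypothesis 2 contrast (group by time, baseline against post-treatment) and gives its purpose: "This interaction comparison will be used to directly test this hypothesis, that the ABC-I group shows greater positive changes" on the outcome measures than the CBT-I group. The Hypothesis 3 contrasts are worded neutrally.

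The PSQI figure is 1.4 points where delta is determined, 1.8 points in the Statistical Analysis paragraph, and 2 points in the sample-size text. The sample-size text uses alpha .05 without saying whether it is one- or two-sided. The Figure 8 caption refers to 95% intervals.

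**The concern.** A hypothesis that ABC-I produces larger gains than CBT-I has a null of zero. A hypothesis that ABC-I is not worse by delta or more has a null of delta. The estimate and its interval are the same in both cases, but the success criterion differs. The quoted sentence is the one that tells the analyst what the Hypothesis 2 contrast is for, and a default interaction contrast from an ANOVA is tested against zero. If the sentence is followed literally, a trial in which the two treatments perform alike would normally fail, and the question Aim 2 asks would not be answered.

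The sentence also conflicts with the sample-size text for Aims 2 and 3, which rests on a margin of about 0.40 SD and offers no assumed advantage for ABC-I. Aims 2 and 3 are not the primary outcomes (section 3.1 gives those as adherence and attrition), but they carry the comparative-effectiveness claim.

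**Working it through.** **The passages side by side.** Section 3.1, the Hypothesis 2 heading, the formal null, Table 12 and the first Statistical Analysis paragraph all point to non-inferiority. One sentence points to superiority. No passage describes superiority as a second step after non-inferiority.

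**The plan's own sample size.** Section 3.8d gives n = 138 for d = 0.40, alpha .05, power .80. With n per arm = 2[(z(1−α) + z(.80))/d]²:
- one-sided .05: 2[(1.645 + 0.842)/0.40]² = 77.3, so 78 per arm, 156 in total;
- one-sided .025 (or two-sided .05): 2[(1.960 + 0.842)/0.40]² = 98.1, so 99 per arm, 198 in total.

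The figure of 138 is not reproduced from the stated inputs. A baseline correlation of about 0.56 with change scores would reach it at one-sided .05, but the plan gives no correlation. That is a separate matter. What counts here is that the calculation uses the margin as its effect size.

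**What the two readings do.** Let D = improvement with CBT-I minus improvement with ABC-I. Non-inferiority requires the upper confidence limit of D to be below delta; superiority requires it to be below 0.

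Inputs: 74 per arm (section 3.1), 146 degrees of freedom, ISI delta = 2 (section 3.8d). The SD of the ISI change is assumed to be 5, since 2 points = 0.40 SD gives 2/0.40 = 5. The plan ties 0.40 to the SD of each outcome measure, not of its change. The two are equal only when 2(1 − ρ) = 1, that is ρ = 0.5 with equal variances, so SD 4 to 8 is also shown.

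SE = 5 × √(2/74) = 0.822. At one-sided .05 the half-width is 1.655 × 0.822 = 1.36. Non-inferiority is then declared if the observed D is below 2 − 1.36 = 0.64, and superiority if it is below −1.36.

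Chance of success with truly equal arms (exact noncentral t, noncentrality 2/SE):

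| SD of change | Non-inferiority, one-sided .05 | Non-inferiority, one-sided .025 |
|---|---|---|
| 4 | 91.7% | 85.6% |
| 5 | 78.1% | 67.6% |
| 6 | 64.6% | 52.2% |
| 7 | 53.4% | 40.8% |
| 8 | 44.8% | 32.7% |

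Superiority succeeds 5% or 2.5% of the time in every row. That is alpha by definition.

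**Nesting.** If the upper limit of D is below 0 it is also below delta, because delta is positive. For one outcome and one alpha, superiority therefore implies non-inferiority.

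**The case against.** The strongest reply is that the plan already settles which test governs. The formal hypotheses, Table 12 and the paragraph just before the quoted sentence all use delta, and that paragraph covers Hypotheses 2 and 3 together. The quoted sentence gives no null value, alpha or decision rule, and it reads like wording carried over from a superiority design. This stands, and it limits the point to a contradiction to be reconciled. It does not remove it: the sentence still assigns the contrast a hypothesis different from the one in the section heading, and nothing later corrects it. The same reply disposes of any complaint about Hypothesis 3, whose neutral wording is covered by the common null.

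A reader might infer that having both wordings inflates error, or lets a favourable test be picked once the data are in. The documents do not support that. The tests are nested on one contrast, so reading the same interval first against delta and then against 0 inflates neither error rate.

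A reader might also take the gap between 78% and 5% as the chance of a wrong result. It is not: a finding of non-inferior but not shown superior is a coherent result, and the 5% is simply alpha.

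Finally, the printed signs of the time contrasts may have suffered in text extraction, and Figure 8 is not shown. The signs, and the Result 3 text that names CBT-I as the non-inferior arm, are clerical checks only.

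**Conclusion.** The contradiction is real and should be fixed. Hypothesis 2 is a non-inferiority hypothesis everywhere except in the sentence that says what its contrast will test. Taken literally, that sentence would leave Aim 2 unanswered in most trials with equal arms: success in 5% of them, against 78% for the intended test (ISI, SD 5, one-sided .05; 92% to 45% for SD 4 to 8). These percentages rest on an assumed SD of change and illustrate the difference between the tests; the contradiction itself depends on no number.

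Two loose ends belong with it. The PSQI decision threshold is not unique (1.4, 1.8 or 2 points). The alpha in the sample-size text has no stated sidedness, while the Figure 8 caption refers to 95% intervals. The plan does not support the stronger reading that Aim 2 has become a superiority aim.

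**What to change.** Replace the sentence with: the Hypothesis 2 baseline-to-post-treatment contrast tests H0: D ≥ delta, where D is improvement with CBT-I minus improvement with ABC-I, and ABC-I is declared non-inferior if the upper confidence limit of D is below delta. State the same rule for the Hypothesis 3 baseline-to-3-month contrast. Allow a superiority test only after non-inferiority has been shown.

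In the same edit:
- give one PSQI margin throughout section 3.8d;
- state one confidence level that matches the one-sided alpha (a 90% interval for .05 or a 95% interval for .025), and use it in both the Figure 8 text and the sample-size text;
- write out the contrast signs and group coding so that improvement means a fall in ISI and PSQI and a rise in sleep percent, and check the Result 3 wording against the figure.

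The cost is a few sentences. No new data are needed, and the rewording does not change the sample size. Choosing one-sided .025 would lower non-inferiority power at SD 5 from 78% to 68%, so that choice should be made knowingly.

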Insomnia symptom severity	Insomnia Severity Index (ISI) ⁴⁴	X	X	X	
Subjective Sleep Quality	Pittsburgh Sleep Quality Index (PSQI) ⁶⁰	X	X	X	
Sleep diary reported sleep efficiency, hours of sleep, nighttime awakenings, daytime sleeping	Daily sleep diaries	X	X	X	
Diagnosis of insomnia disorder	Survey of ICSD diagnostic criteria	X	X	X	
Sleep effort	Glasgow Sleep Effort Scale ⁴⁵	X	X	X	
Secondary outcome measures					
Health-related quality of life	MOS, 12-item short-form health survey (SF-12) ⁷⁴	X	X	X	

Insomnia Severity Index (ISI):⁴⁴ The ISI is a 7-item instrument using Likert-type scales that measures perceived severity of insomnia symptoms from 0 (not at all) to 4 (very much). The total score ranges from 0 to 28, with higher scores indicating greater insomnia severity. The ISI correlates well with scores on the PSQI ($r=0.67$), and with sleep diary measures ($r's=0.32-0.91$).⁴⁴ Key variable: ISI total score

Pittsburgh Sleep Quality Index (PSQI):⁶⁰ The PSQI is a widely-used 18-item questionnaire that assesses sleep quality and disturbances over the last month. The PSQI measures sleep quality, sleep latency, sleep duration, sleep efficiency, sleep disturbances, use of sleeping medication, and daytime dysfunction. The PSQI has a sensitivity for distinguishing normal and abnormal sleepers of 89.6%, and a specificity of 86.5% ($\kappa=0.75$, $p<.001$).⁶⁰ The PSQI also has good test-retest reliability over 1 month ($r=0.85$; $p<.001$).⁶⁰ We will use the 3-factor scoring system, which has been shown to have superior psychometric properties compared to the original 7-factor scoring system.⁷⁸ Key variables: PSQI total score and 3 subscale scores

Daily sleep diaries: Participants will complete a sleep diary for one week at baseline, post-treatment assessment and at the three month follow-up assessments. We will use the sleep diary developed in our pilot study, which is based on the American Academy of Sleep Medicine Consensus Sleep Diary⁷⁹ and was adapted using a cognitive interviewing process⁸⁰ during our pilot project. Key outcome variables: Self-reported sleep efficiency (time asleep out of total time in bed), hours of sleep, time to fall asleep, time awake at night, and number of nighttime awakenings

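### The non-inferiority rule in 3.8d applies one inequality and one time contrast to outcomes that improve in opposite directions, so literal coding reverses at least one of the three tests per hypothesis

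*Combined protocol and SAP*

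**What the plan says.** All references are to the combined protocol and SAP.

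- **Definition in words (3.8d, Description of analysis).** Non-inferiority means that "the efficacy of ABC-I is no more than δ units less than CBT-I". Larger is better on this scale, whatever the instrument.
- **Formal null (same paragraph).** A "one sided null hypothesis that the difference between CBT-I and ABC-I is greater than or equal to δ", against the alternative that it is smaller. The Statistical Analysis paragraph repeats this null with positive margins for ISI, PSQI and sleep percent. It does not change the inequality by outcome or reverse-score any of them.
- **Hypothesis 2 contrast.** Treatment group is crossed with "time using a 1-1-0 contrast for the time factor". The same contrast serves every outcome, and the text says that it tests the hypothesis directly.
- **Hypothesis 3 main contrast.** It is formed by "applying a -1 0 1 contrast to time and interacting that with treatment group", again for every outcome.
- **Scoring (3.5d).** For ISI the plan says "higher scores indicating greater insomnia severity". For PSQI it gives no direction, but reports a positive correlation with ISI (r=0.67). Nighttime sleep percent is better when higher, by its nature.
- **Figure 8 text, written for ISI.** It speaks of one arm's mean being greater without saying what the mean measures. In Result 3, where the ABC-I mean is greater, it ends with "establishing the non-inferiority of CBT-I".

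**The concern.** The null has the right sign only if a larger analysed value means more benefit. ISI falls with benefit and sleep percent rises, so one contrast with one inequality cannot orient both correctly. The main Hypothesis 3 contrast is follow-up minus baseline, which makes a good ISI result negative. The Hypothesis 2 string, read as 1 -1 0, is baseline minus post-treatment, which makes a good sleep-percent result negative.

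A reversed non-inferiority test passes more easily the worse ABC-I is, and tends to fail when ABC-I is clearly better. An analyst who coded the contrasts as printed and compared them with the stated margin could draw the opposite conclusion on some outcomes in Aims 2 and 3.

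**Working it through.** The plan gives no figure of its own on this point. The check has two parts.

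**1. Sign of each test.** Take a participant who improves by one unit and stays improved. Relative to baseline, her (baseline, post-treatment, follow-up) profile is (0, -1, -1) for ISI and PSQI and (0, 1, 1) for sleep percent. Multiply by the contrast and add. A negative result means that benefit is coded as negative, so the stated null points the wrong way.

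| Contrast | ISI | PSQI (assumed higher = worse) | Sleep percent |
|---|---|---|---|
| H2 read as (1, -1, 0) | +1 | +1 | -1, wrong |
| H2 read as (-1, 1, 0) | -1, wrong | -1, wrong | +1 |
| H3 as printed (-1, 0, 1) | -1, wrong | -1, wrong | +1 |

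- Contrasts as printed: 1 + 2 = 3 of 6 wrong.
- H2 string taken as a misprint of -1 1 0: 2 + 2 = 4 of 6 wrong.
- Both contrasts as baseline minus later visit: only sleep percent is wrong, 2 of 6. This requires changing the Hypothesis 3 contrast that is printed.
- Every outcome scored as improvement, as the verbal definition implies: 0 of 6.

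Reversing the order of the groups flips every sign in the table. Each row has at least one sign of each kind, so at least one of the three outcomes per hypothesis is still wrong on any raw-score coding.

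**2. Consequence of a wrong sign, for ISI.** Inputs: 74 per arm (3.4c); margin 2 points, equated in 3.8d with 0.40 SD, so SD = 2/0.40 = 5. That this SD applies to the change score is an assumption. Test level: one-sided 5%; 3.8d gives alpha .05 without saying one- or two-sided.

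- SE = 5 × sqrt(2/74) = 0.822.
- P(declare non-inferior) = Φ((2 - D)/SE - 1.645), where D is the expected CBT-I minus ABC-I value as coded.
- ABC-I truly worse by 2, correct coding: D = +2, Φ(-1.645) = 5%.
- ABC-I truly worse by 2, reversed coding: D = -2, Φ(4/0.822 - 1.645) = Φ(3.22) = 99.9%.
- ABC-I truly better by 2: the two figures change places, 99.9% with correct coding and 5% with reversed coding.
- At one-sided 2.5%, which matches the 95% interval in the Figure 8 caption, 99.9% becomes 99.8% and 5% becomes 2.5%.

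Range for the SD: if 5 is the SD at a single visit and visits are uncorrelated, the SD of change is 5 × sqrt(2) = 7.07 and SE = 7.07 × sqrt(2/74) = 1.16. The reversed test then passes Φ(4/1.16 - 1.645) = about 96%; the correct test still passes 5%.

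**Worked case.** At follow-up, ISI changes by -8 on CBT-I and -5 on ABC-I. Coded literally, the difference is -8 - (-5) = -3, with upper bound -3 + 1.645 × 0.822 = -1.65. That is below 2, so ABC-I is declared non-inferior although it is 3 points worse. Coded as improvement, the difference is 8 - 5 = +3 with upper bound 4.35, and non-inferiority is not declared.

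**The case against.** The strongest reply is that the null belongs to the efficacy scale on which it was introduced. The same part of 3.8d says that treatment effects are being compared, expresses the ISI margin as a difference between treatment effects, and in Table 12 words the null as ABC-I being inferior. Results 1 and 2 of the Figure 8 text fit this: withholding non-inferiority from ABC-I because the CBT-I mean is greater makes sense only if the mean is improvement, since a greater raw ISI under CBT-I would favour ABC-I. The figure itself is not visible in the text available here, so an axis label may say so. The sign of an ANOVA contrast is also often only a coding convention.

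Much of this stands. It shows what was intended, and on that reading no test is reversed.

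It does not settle the matter, because the contrasts are the operational instruction and conflict with that intent. The plan says that the Hypothesis 2 contrast tests its hypothesis directly, assigns each contrast to every outcome, and nowhere says that scores are re-expressed as improvement. It also describes the Hypothesis 2 comparison as showing greater positive change with ABC-I, which is a superiority statement. Result 3 draws its conclusion about the wrong arm.

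It is also fair to say that the Hypothesis 2 string is badly set. The other two contrasts in the section run later minus earlier, so -1 1 0 may have been meant. A reader should therefore not take it as established that the Hypothesis 2 and 3 contrasts run in opposite directions. The Hypothesis 3 contrast is unambiguous, and it alone reverses ISI (and PSQI, on the assumed direction).

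**Conclusion.** The plan is wrong as written, with moderate severity. Its printed contrasts and single inequality do not implement its own definition of non-inferiority for all outcomes. Applied literally to raw scores, at least one of three outcomes per hypothesis is tested in the wrong direction: 3 of 6 tests as printed, or 4 of 6 if the Hypothesis 2 string is a misprint.

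A reader might infer that half or more of the tests will pass an inferior ABC-I. The documents do not support that. The verbal definition, Table 12 and Results 1 and 2 all point to an improvement scale on which none of the six is reversed. The 99.9% is what a miscoded test would do; it is not the operating characteristic of the intended analysis.

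The conclusion rests on an assumed PSQI direction, inferred from its positive correlation with ISI; on an SD of change of 5; and on a one-sided 5% level. Only the size depends on the last two. Section 3.1 makes adherence and attrition the primary outcomes, which limits the weight of this point, but these tests carry the trial's whole non-inferiority claim.

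**What to change.** In 3.8d:

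1. Define each analysed outcome as improvement from baseline, positive meaning better: baseline minus later visit for ISI and PSQI, later visit minus baseline for sleep percent. State the PSQI scoring direction in 3.5d.
2. Use the same orientation for the Hypothesis 2 and Hypothesis 3 contrasts, including the secondary post-treatment to follow-up contrast, and correct the string 1-1-0.
3. Keep the null as improvement on CBT-I minus improvement on ABC-I at or above the margin. State that the upper confidence bound of that difference is compared with the margin, and give its level.
4. Restate the four Figure 8 results on the improvement scale, so that Result 3 concludes non-inferiority of ABC-I.

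The cost is a few sentences. No new data and no extra participants are needed.
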